### *3.2.3.6 Presence of Antibodies to Botulinum Toxin Type A*

See section 3.2.11 for details of the analyses for BTX-A-Abs.

3.2.3.7 Subgroup Safety Analyses

Additional subgroup analyses will be conducted on the Safety population across all treatment cycles for **study limb dose** and **total body dose** (using the dose groups specified in Section 3.2.1.2 as administered in the specified Treatment Cycle):

- Overall AE summary table
- Summary table by SOC and PT for TEAEs
- Summary table by SOC and PT for SAEs and TEAEWDs
- Summary table by SOC and PT and by intensity for TEAEs
- Summary table by SOC and PT and by causality for TEAEs
- Summary table for all TEAEs occurring for  $\geq 3\%$  of subjects and more than 1 subject in at least one treatment group at the PT level

by:

- Sex (Male or Female)
- Age group (2 9 years or 10 17 years)
- Botulinum toxin status (Naïve or Non-naïve)
- BMI category (Less than the 5th percentile or 5th percentile to less than the 95th percentile or equal to/greater than the 95th percentile).

Shift from baseline tables of the number and percentage of subjects with low, normal or high values for alkaline phosphatase and HbA1c will be repeated by age group.

3.2.4 Missing Data and Outliers

#### 3.2.4.1 Missing Data

## **Efficacy**

In order to assess the impact of the missing values of the primary efficacy endpoint for the withdrawals between the baseline visit and Treatment Cycle 1, Week 6 visit, the primary analysis performed on the assessed values of the primary efficacy endpoint will be completed with a sensitivity analysis performed on the population of all randomised subjects. Within that population, any missing assessment on the MAS at Treatment Cycle 1, Week 6 visit will be imputed with the assessment on the MAS at the baseline visit (conservative approach). In case any baseline assessment on the MAS is missing, the baseline assessment is imputed with the average baseline assessment on all randomised subjects.

The results of the sensitivity analysis will be taken into account to assess the robustness of the results of the primary analysis.

• In view of registration in the US only

In order to assess the impact of the missing values of the first secondary efficacy endpoint for the withdrawals between the baseline visit and the Treatment Cycle 1, Week 6 visit as well as for subjects not assessed in the mITT population, the primary analysis performed on the assessed values of the first secondary efficacy endpoint will be completed with the following two sensitivity analyses performed on the population of all randomised subjects:

- First sensitivity analysis: any missing assessment on the PGA at Treatment Cycle 1, Week 6 visit will be imputed with the assessment 'markedly worse' (intermediate conservative approach)
- Second sensitivity analysis: any missing assessment on the PGA at Treatment Cycle 1, Week 6 visit for a subject in a higher dose Dysport group will be imputed with the assessment 'markedly worse' and any missing assessment on the PGA at Treatment Cycle 1, Week 6 visit for a subject in the low dose Dysport group will be imputed with the assessment 'markedly improved' (most conservative approach).

The results of the two sensitivity analyses will be taken into account to assess the robustness of the results of the primary analysis.

#### **Safety**

If a value required a retest (for laboratory values, vital signs and ECG) the closest non-missing reliable value to the scheduled visit will be used in the summary tables. An assessment will be considered reliable if it is performed without any technical problem and if the result is within the range of plausible values.

For adverse events with missing information for the intensity and causality the value will not be replaced and will be summarised as a separate category.

### All data

If there is a significant number of missing values for a subject (or if there is confirmed data appearing spurious), a decision will be made following consultation with the sponsor regarding the handling of these data in summaries, prior to breaking the blind.

Any repeat or additional assessments performed will be included in the individual subject data listings.

All issues relating to missing data will be discussed at the BDRM.

## 3.2.4.2 Missing or Incomplete Dates

In all listings, missing or incomplete dates should be left as they have been recorded. However, for calculation/sorting/assignation based on dates, the following methods will be used:

- (1) The most conservative approach will be systematically considered (i.e. if the onset date of an AE/concomitant medication is missing/incomplete, it is assumed to have occurred during the study treatment phase (i.e. a TEAE for AEs) except if the partial onset date or the stop date indicates differently).
- (2) Similarly, if the onset time of an AE is missing then a conservative approach will again be taken, so that it is assumed to be a TEAE unless the onset date, stop date, or stop time indicates differently.
- (3) A missing/incomplete date of medical history or disease diagnosis will be assumed to have occurred before any study treatment.
- (4) A medication with partial start and stop dates will be considered as concomitant treatment, except if the partial dates indicate differently.
- (5) Where this is possible, the derivations based on a partial date will be presented as superior inequalities (i.e.: for an AE started in FEB2004 after the administration performed on 31JAN2004, the days since last dose will be "≥2", similarly the duration of ongoing AEs or medication will be "≥xx" according to the start and last visit dates).
- (6) If an AE or SAE onset date is partial or missing, the event will be allocated to the first treatment where onset could have occurred (taking into account date and time stopped).
- (7) If the start date of a medication is partial or missing, the medication will be assigned to the most recent treatment received on or before the medication start date (taking into account date stopped).

## 3.2.4.3 Outliers

In the event of any remaining unresolved data issues at the time of the BDRM, their impact on the statistical analyses will be assessed and any corrective action will be implemented prior to unblinding.

# 3.2.5 Subject Disposition

All disposition data will be included in the subject disposition listings and all summary tables for subject disposition will be based on the Randomised population, unless otherwise specified.

A listing of all visit assessment dates (relative days) will be presented by subject ID and Treatment Cycle. Subject disposition data (including date of informed consent/screening/randomisation/first study drug administration, last Treatment Cycle/last visit/status at end of study, and study duration will be listed by subject ID.

An overall summary of subject disposition by treatment group of Treatment Cycle 1 will be displayed for all screened subjects with the numbers and percentage of subjects screened, screen failures, randomised, randomised and treated, and the size of the mITT, PP and Safety populations. The numbers and percentage of subjects received study medication, completed Treatment Cycle, and withdrawn from the Treatment Cycle will be displayed by treatment group of each Treatment Cycle (1, 2, 3 and 4).

A summary table will also display the count and percent of subjects by country, country/centres (and country/pooled centres if needed) by treatment group of Treatment Cycle 1.

For the mITT population, a summary table will present by treatment group the number of subjects assessed at each Treatment Cycle and scheduled visit.

Counts and percents of subjects with any major protocol deviation and any major protocol deviation impacting the PP population will be tabulated by treatment group. Reasons for exclusion from the Safety, mITT and PP populations will be presented in summary tables by treatment group of Treatment Cycle 1 for the randomised and treated subjects.

All major protocol deviations identified prior to unblinding together with the reasons for exclusion from the analysis populations will be listed by subject ID. Also, any major protocol deviations impacting the PP population will be presented in an additional listing.

In addition to above, listings will present screening failures, violated inclusion criteria and fulfilled exclusion criteria, and randomisation information by subject ID. Screening failures and study withdrawals will also be listed by subject ID.

A summary table will present the overall study duration overall and by treatment group.

### 3.2.6 Withdrawals

All information on subject withdrawals will be included in the listings and all summary tables for subject withdrawals will be based on the randomised population. Discontinued subjects will be listed and a summary table of the number and percentage of subjects who withdrew from the study and the reasons for withdrawal will be presented by treatment group and overall and for each Treatment Cycle.

### 3.2.7 Demographic and Baseline Characteristics

All demographic data and data on baseline characteristics will be included in the listings and summary tables, listings will be based on the Randomised Population, tables will be based on the mITT population. Summary tables will be presented by treatment group of Treatment Cycle 1.

The overall summary table will be repeated for the Safety population. It will also be repeated for the PP population.

All demographic and baseline characteristics will be listed by subject ID. This includes:

- Demographics
- Neurological examinations
- Gross motor function classification system
- Tanner grading scale

Descriptive statistics will be provided for the following demographic and baseline characteristics, by treatment group:

- Sex (Male or Female)
- Race (Asian, Black / African American, Caucasian / White, Native Hawaiian / Other Pacific Islander, American Indian / Alaska Native, or Multiple Race)
- Ethnicity (Hispanic / Latino, Not Hispanic / Latino)
- Age (years)
- Age group (2 9 years or 10 17 years)

- Height (cm)
- Weight (kg)
- Body mass index (kg/m^2)
- Body mass index at baseline in categories (Less than the 5th percentile, 5th Percentile to less than the 95th percentile, Equal to or greater than the 95th percentile)
- Botulinum toxin status (Naïve or Non-naïve)
- Tanner grading scale (I, II, III, IV, or V)
- Baseline MAS score in the PTMG
- Baseline original MAS score in the PTMG (0, 1, 1+, 2, 3, 4)
- Baseline MAS score in the elbow flexors
- Baseline original MAS score in the elbow flexors (0, 1, 1+, 2, 3, 4)
- Baseline MAS score in the wrist flexors
- Baseline original MAS score in the wrist flexors (0, 1, 1+, 2, 3, 4)
- Baseline MAS score in the finger flexors
- Baseline original MAS score in the finger flexors (0, 1, 1+, 2, 3, 4)
- Geographical location (US or non-US)
- Gross motor function classification system level (1, 2 or 3)

The descriptive statistics will also be repeated, on the mITT population, by each of the following subgroups:

- Sex (Male or Female)
- Age group (2 9 years or 10 17 years)
- Botulinum toxin status (Naïve or Non-naïve)
- Geographical location (US or non-US)

Demographic and baseline characteristics will not be compared between treatment groups by formal statistical testing and only 95% CIs will be calculated.

### 3.2.8 Medical and Surgical History

All medical and surgical history data will be included in the listings and summary tables, listings will be based on the Randomised population and tables will be based on the mITT population.

## 3.2.8.1 Cerebral Palsy History

Descriptive statistics will be provided for the following:

- Type of paralysis (Hemiparesis, Paraparesis, Diparesis or Tetraparesis)
- Diagnosis of CP as defined by Rosenbaum [2] (Yes or No)
- Presence of severe athetoid or dystonic movements in the targeted upper limb (Yes or No)
- Intensity of athetoid or dystonic movements (Mild, Moderate or Severe)
- Hypertonia assessment tool responses (Positive or Negative responses to seven assessments designed to measure dystonia, spasticity and rigidity)
- Manual ability classification system level (MACS or mini-MACS) (1, 2, 3, 4 or 5).

Listings will present all data collected on subjects' CP history (including Hypertonia assessment tool [3] and MACs (or mini-MACS)) for the Randomised Population, by subject ID.

3.2.8.2 Other Significant Medical and Surgical History

Other significant medical and surgical history will be collected on the electronic case report form (eCRF), and will be coded using MedDRA.

Listings will present all data collected by subject ID, primary SOC, PT and verbatim text.

For all significant medical and surgical history a frequency table of the number and percentage of subjects will be provided by primary SOC and PT, for each treatment group of Treatment Cycle 1.

## 3.2.9 Study Exposure/Treatment Profile

All data on subject exposure will be included in the listings. A per subject listing will present for each study treatment the cycle duration (in days), study limb dose, non-study upper limb dose, lower limb dose, and total body dose in U/kg. Details of the study drug preparation and administration (date / time of administration, muscle targeting technique, any difficulties during drug administration, muscles injected by limb, volume and dose (U/kg) administered) will be presented in a separate listing. The PTMG will be flagged.

Tables will be based on the safety population.

## 3.2.9.1 Summary of Exposure to IMP Across the Study

Across the study, irrespective of number of study treatments received, the following will be summarised by dose group using the **study limb dose** (as administered in Treatment Cycle 1, see Section 3.2.1.2 for dose groups):

- Summary statistics of duration of IMP exposure from initial Study Treatment 1 to EOS/EW
- Number and percent of subjects with duration between Study Treatment 1 and EOS/EW of:
  - a) < 16 weeks
  - b) At least 16, 22, 28, and >48 weeks.

# 3.2.9.2 Exposure During Fixed Dose Treatment Cycle 1 and over Repeat Treatments

The following will be summarised by dose group using the **study limb dose** for the fixed dose Treatment Cycle 1 (as administered in Treatment Cycle 1, see Section 3.2.1.2 for dose groups):

- Summary statistics of duration of treatment interval in weeks between initial Study Treatment 1 and Study Treatment 2, or EOS/EW
- Number and percent of subjects with duration between Study Treatment 1 and Study Treatment 2 or EOS/EW of:
  - a) < 16 weeks
  - b) At least 16, 22, 28, and >48 weeks.

For Treatment Cycle 2, 3, and 4 corresponding summary statistics will be provided for treatment intervals and durations between Study Treatment 2 and 3 (or EOS/EW), and Study Treatment 3 and 4 (or EOS/EW). Summary tables will be presented by dose group using the study limb dose for Repeat Treatment (as administered in the specified treatment cycle, see Section 3.2.1.2).

## 3.2.9.3 Summary of Location of Treatment

For each Treatment Cycle (Treatment Cycle 1, 2, 3 and 4) and overall, the number and percent of subjects treated in each of the following categories will be presented

by dose group using the **study limb dose** (administered in the specified treatment cycle, using the dose groups specified in Section 3.2.1.2):

- Study limb (left or right)
- PTMG (elbow or wrist flexors)
- Study limb only
- Study limb and non-study upper limb
- Study limb and lower limb(s)
- Study limb, non-study upper limb and lower limb(s)

In addition summary statistics will be presented for dose administered to study limb, non-study upper limb, lower limb(s), and total body.

For Treatment Cycle 1 this will only include treatment of the study limb as no other limb could be treated.

The table will be repeated for all subjects having kept the same PTMG throughout the study.

Overall treatment cycles combined, summary statistics will be presented for the dose administered per treatment cycle to study limb, non-study upper limb, lower limb(s), and total body. Additionally, summary statistics will be presented for the average and cumulative dose administered per subject to study limb, non-study upper limb, lower limb(s), and total body.

For each Treatment Cycle (Treatment Cycle 1, 2, 3 and 4) and overall, the following will be summarised, regardless of PTMG:

- Number and percent of subjects treated in each upper limb and lower limb muscle. For the elbow flexors (brachialis and brachioradialis) and wrist flexors (flexor carpi radialis and flexor carpi ulnaris), this will be presented for each muscle as well as for each muscle group. The upper limb muscles will be presented separately for the study and non-study limb.
- Summary statistics for dose administered to each upper and lower limb muscle. The upper limb muscles will be presented separately for the study and non-study limb.

For Treatment Cycle 1 only the study limb will be treated, non-study upper limb and lower limb(s) can be treated at Treatment Cycle 2, 3, and 4.

### 3.2.9.4 Exposure to Specific Treatments

The following will be presented by study limb dose for subjects who received a Dysport Dose of 8 and/or 16 U/kg.

- Number and percent of subjects receiving
  - a) At least 1 injection of study treatment
  - b) At least 2 injections of study treatment
  - c) At least 3 injections of study treatment
  - d) 4 injections of study treatment.
  - Number and percent of subjects receiving
  - a) 2 consecutive injections of study treatment
  - b) 3 consecutive injections of study treatment
  - c) 4 consecutive injections of study treatment.

In addition for subjects who received a Dysport Dose of **at least 8 or at least 16** U/kg the number and percent of subjects receiving

a) 2 consecutive injections of study treatment within 6 months

b) 4 consecutive injections of study treatment within 12 months will be presented.

## 3.2.10 Prior and Concomitant Therapies

All data on prior and concomitant therapies will be included in the listings and summary tables, listings will be based on the Randomised Population and tables will be based on the mITT population.

For prior and concomitant medications the sponsor will use the latest version of the World Health Organisation Drug Dictionary (WHO-DD) in effect within the sponsor company at the time of database lock.

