Laboratory test results will be recorded by the central laboratory and provided to the study Sponsor, and to the study sites for evaluation of clinically significant changes. All clinically relevant abnormal laboratory tests occurring during the study will be repeated at appropriate intervals until they return to baseline or to a level deemed acceptable by the Investigator and the Sponsor's medical monitor (or his/her designated representative), or until the abnormality is explained by an appropriate diagnosis. See Section 10.1.5 for abnormal laboratory tests that should be recorded as AEs in the eCRF.

8.2.6 *Prior and Concomitant Medications*

Prior and concomitant medications will be included as a safety evaluation in this study and will be monitored from the time that the child's parent(s)/guardian(s) give informed consent to the end of the study (as defined in Section 4.3.2).

8.2.7 *Body Weight and Height*

Body weight will be measured at screening, at Day 1 of each treatment, at Week 16 of each treatment and at the end of study visit or early withdrawal.

Height will be measured at Day 1 of Treatment 1, at Week 16 of each treatment and at the end of study visit or early withdrawal.

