11.2.1 Populations Analysed

For the efficacy analyses, the primary population will be the mITT population, a secondary population of interest will be the PP population.

The safety analyses will be performed based on the safety population.

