11.4.4 Safety Evaluation

The safety endpoints of the study are:

- Treatment emergent adverse events.
- Vital signs (systolic and diastolic BP and HR): absolute values and change from Baseline at each visit to the study centre.
- Body weight and height: absolute values and change from baseline at Week 16 of each treatment and at the end of study visit or early withdrawal.
- Clinical chemistry (including serum ALP - total and bone isoenzyme, and glycosylated HbA1c): absolute values and change from Baseline at Treatment 1, Week 16 (serum ALP - total and bone isoenzyme, and HbA1c only) and at the end of study visit or early withdrawal.
- Presence of BTX-A-Abs at baseline and at the end of study visit or early withdrawal.
- A 12-lead ECG: absolute values and change from Baseline in ECG parameters and morphology at Treatment 1, Week 6 and at the end of study visit or early withdrawal.

All safety data will be included in the safety data listings and summary tables will be produced on the safety population. Descriptive statistics will be provided for the safety endpoints.

Adverse Events

Adverse events will be coded using the Medical Dictionary for Regulatory Activities (MedDRA, version in force at the time of database freeze).

All AEs reported during the study will be presented in a listing which will be sorted by treatment group, subject ID, primary system organ class (SOC), preferred term, verbatim text and start date.

Listings of all SAEs, AEs leading to withdrawal and deaths reported during the study will also be presented by treatment group and subject ID.

A TEAE is defined as any AE that occurs during the treatment phase of this study if:

- (1) It was not present prior to the first of intake of study treatment, or
- (2) It was present prior to the first intake of study treatment but the intensity increases during the treatment phase of this study.
- (3) It was present prior to receiving the first dose of study treatment, the intensity is the same but the drug relationship became related during the active phase of the study.

An overall summary table of all AEs will be presented. In summaries of intensity, causality, and causality combined with intensity, subjects may be reported in more than one category in these tables according to how many different levels of intensity and causality are associated to the AEs they experience.

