Summary statistics on the duration of QT/QTc interval and HR will be presented overall and by treatment group for each scheduled assessment visit and for both actual values and changes from baseline. Baseline values for each treatment group will be defined as the measurements collected at screening.

The number and percentage of subjects with duration of QT/QTc interval within the following three ranges of interest will also be presented overall and by treatment group for each scheduled assessment visit:

- >450 to 480 msec.
- >480 to 500 msec.
- >500 msec.

The number and percentage of subjects with an increase from baseline in the QT/QTc interval of >30 msec and >60 msec will also be presented overall and by treatment group for each scheduled post baseline assessment visit.

The number and percentage of subjects with any of the following ECG abnormalities will be provided overall and by treatment group for each scheduled assessment visit:

- Arrhythmias.
- Second degree AV block
- Third degree AV block.
- ST segment abnormalities.
- T-wave abnormalities.
- U-wave abnormalities.
- Myocardial infarction.
- Right bundle branch block
- Left bundle branch block.

Prior and Concomitant Medications

Prior and concomitant medications will be coded according to the World Health Organisation Drug Dictionary (version in force at the time of database freeze).

The date of Day 1 will be used as the cut off date for the definition of a prior and a concomitant medication. A medication that started before the cut off date and is continuing will be considered as both prior and concomitant medications.

The number and percentages of subjects will be provided overall and by treatment group for prior and concomitant medications sorted by drug class and preferred drug name.

A listing will present by treatment group the prior and concomitant medications sorted by drug class and preferred drug name. Prior and concomitant medications will be flagged in the listing.

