# 2 SUBJECT POPULATIONS (ANALYSIS SETS)

## 2.1 Efficacy

#### 2.1.1 Modified Intent-to-treat Population

The modified Intent-to-treat (mITT) population will consist of all randomised subjects who received at least one injection of the study treatment and had a MAS score in the PTMG assessed both at baseline and at Treatment Cycle 1, Week 6. The mITT population will be analysed using the dose group as randomised, regardless of treatment actually received.

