# 2.2 Safety Population

The safety population will consist of all randomised subjects who received at least one injection of study treatment, analysed using dose actually received.

In case a subject has not received the planned dose of 1.6 ml in the study limb the actual study limb dose will be calculated based on the actual volume received.

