# 3.2.3 Safety

All safety data will be included in the safety data listings and summary tables will be based on the safety population. Across all treatment cycles summary safety tables

will be presented by the dose received in the study limb in the specified Treatment Cycle. For the fixed dose Treatment Cycle 1 selected tables will also be presented by exact dose received. For analyses over repeat treatments by Treatment Cycle, selected tables will also be presented by total body dose received.

Safety tables will be presented by the treatment groups specified in Section 3.2.1.2.

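### The SAP tabulates prior and concomitant medication on mITT although the protocol places these tables under safety, on the safety population, so treated children without a Week 6 MAS are in the main AE tables but not in the medication tables

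*SAP*

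**What the plan says.** The protocol treats medication as safety data. Section 8.2.6, within the safety evaluations, states: "Prior and concomitant medications will be included as a safety evaluation in this study". Section 11.2.1 sets the general rule: "The safety analyses will be performed based on the safety population". Section 11.4.4, Safety Evaluation, repeats it for tables: "All safety data will be included in the safety data listings and summary tables will be produced on the safety population". The same section then specifies the medication summary: "The number and percentages of subjects will be provided overall and by treatment group for prior and concomitant medications". It names no other analysis set for that summary.

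The SAP uses a different set. Section 3.2.10, Prior and Concomitant Therapies, says "listings will be based on the Randomised Population and tables will be based on the mITT population". SAP 2.1.1 limits mITT to randomised, injected subjects who "had a MAS score in the PTMG assessed both at baseline and at Treatment Cycle 1, Week 6". The safety set in SAP 2.2 has no such condition: "The safety population will consist of all randomised subjects who received at least one injection of study treatment, analysed using dose actually received". For the AE and other safety tables, SAP 3.2.3 says: "All safety data will be included in the safety data listings and summary tables will be based on the safety population".

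SAP section 5 lists changes from the protocol. In its visible part it does not mention a change of population for the medication tables.

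**The concern.** Two documents give the same table two different populations, and the SAP is the one that will be programmed. The children who fall between the two sets are not a random few. Protocol 6.4 lists, among the reasons for withdrawal, an adverse event and the need for a treatment that the protocol does not allow. A child who leaves before Week 6 for either reason has no Week 6 MAS and so is outside mITT. That child's medication is of particular interest to a safety reader.

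The mismatch also affects interpretation. Under Protocol 10.1.4 and SAP 3.2.3.1, concomitant medication is one of the alternative explanations weighed when an event is judged as possible remote spread or hypersensitivity. A reader who sets the AE tables beside the medication tables would be comparing percentages with different denominators, and nothing in the SAP text warns of this.

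**Working it through.** The documents state no figure for this point, so there is none to reproduce. The check compares set definitions and then sizes the gap under an assumption.

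**Step 1: the sets side by side**

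| Item | Protocol | SAP |
|---|---|---|
| Status of medication | Safety evaluation (8.2.6) | Filed under Other Assessments (1.3.2.3) |
| Set for medication tables | Safety population (11.4.4) | mITT (3.2.10) |
| Set for AE tables | Safety population (11.4.4) | Safety population (3.2.3) |
| Set for medication listings | Listed by treatment group, no set named (11.4.4) | Randomised population (3.2.10) |

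**Step 2: who is in one table and not the other**

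Both sets require randomisation and at least one injection. mITT adds a MAS score in the primary targeted muscle group at baseline and at Cycle 1 Week 6. The difference (safety set minus mITT) is therefore every treated child missing either score. Entry requires a baseline MAS of at least 2 (Protocol 6.2), so in practice Week 6 decides.

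**Step 3: which cycles are affected**

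- A child who withdrew before Week 6 has data in Cycle 1 only. That child is missing from the Cycle 1 medication tables and has nothing to contribute to later cycles in any table.
- A child who missed only the Week 6 MAS and stayed in the study is outside mITT permanently. That child's medication is also missing from the Cycle 2 to 4 tables.

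**Step 4: size**

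Inputs: 210 randomised, 70 per group (Protocol 11.3, SAP 1.3.4). SAP 3.2.4.1 anticipates withdrawals before Week 6 but gives no rate. I assume that all 210 are treated and that a fraction d has no Week 6 MAS. The number affected is 210 × d.

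- d = 0: none, and the two sets coincide.
- d = 1%: 210 × 0.01 = 2.1, about 2 children.
- d = 5%: 210 × 0.05 = 10.5, about 11 children.

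The effect on an overall percentage follows from p(safety) = (1 − d) × p(mITT) + d × p(excluded). The shift is d × [p(excluded) − p(mITT)], which cannot exceed d. At d = 5% an overall medication percentage moves by at most 5 percentage points. Within one group the bound could be higher: if all 10.5 fell in a single group of 70, d there would be 10.5 / 70 = 15%.

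**Step 5: is it declared or repeated elsewhere?**

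The visible part of SAP section 5 declares a change of population for the missing-data sensitivity analyses, so its authors regarded a change of set as something to declare. This one is not there. SAP 3.2.7 repeats the demographic summary for the safety population, and SAP 3.2.9 puts the exposure tables on it. No such repeat is stated for medication.

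**The case against.** The best counter-argument is that little is lost. Listings cover the Randomised population, and SAP 3.2.10.2 adds separate listings for spasticity medication and for potentially prohibited medication. Withdrawal reasons are tabulated on the randomised population (SAP 3.2.6), adverse events leading to withdrawal on the safety population (3.2.3.1), and reasons for exclusion from mITT in the disposition tables (3.2.5). The sponsor judges events of special interest case by case before unblinding. Medication is not a listed safety endpoint (Protocol 4.2.2), and no efficacy test or AE rate depends on these tables. All of this stands. It limits the consequence to the summary tables but does not remove the contradiction with Protocol 11.4.4.

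Redaction also limits what can be said. The SAP table index is blacked out and section 5 has a gap, so an extra safety-population table or a declaration cannot be ruled out. The readable SAP text contains neither.

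A reader might infer more than the documents support:

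- *That the non-drug therapy and surgery tables also contradict the protocol.* Protocol 8.2.6 and the table specification in 11.4.4 name medications only. Physiotherapy, occupational therapy and splints also bear on efficacy, so mITT is defensible for them.
- *That botulinum toxin history (SAP 3.2.10.1) should move too.* It is pre-study history, and Protocol 11.4.1 puts baseline characteristics on mITT.
- *That the excluded children vanish from the medication tables in all four cycles while staying in every AE table.* Step 3 shows this is false for children who withdrew before Week 6. The exact-dose AE tables in SAP 3.2.1.2 and 3.2.3.1 also leave out anyone who did not receive precisely the stated dose.
- *That SAP 3.2.10.2 mixes actual-dose grouping with an efficacy set.* Its rule of using the most recent dose on or before the start date can be read simply as a way to place records in cycles.

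**Conclusion.** The point holds for prior and concomitant medication. The protocol assigns these tables to the safety population, the SAP assigns them to mITT, and the readable SAP neither declares nor compensates for the change. As written, treated children without the required MAS scores contribute to the main AE tables but not to the medication tables.

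The effect is probably small: about 2 to 11 of 210 children if 1% to 5% lack a Week 6 score, and none if no score is missing. That range is an assumption. The contradiction itself depends on no figure. No primary or secondary efficacy result is touched. The change should still be made, because the SAP departs from a stated protocol rule, the affected children may be informative for safety, and the correction costs almost nothing.

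**What to change.** In SAP 3.2.10 and 3.2.10.2, base the prior and concomitant medication tables on the safety population by dose received, or keep the mITT versions and repeat the tables on the safety population.

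For consistency, the concomitant non-drug therapy and surgical procedure tables may also be repeated on the safety population, with the mITT versions kept as efficacy context. This part is optional, since the protocol does not require it. Leave Botulinum Toxin History (3.2.10.1) on mITT as baseline data.

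The cost is a changed population label in the SAP text and table shells, or a few extra tables. No new data or derivation is needed.
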